4.2.3.5 Supportive secondary safety endpoints

- Number of treatment emergent adverse events (AEs) during 16 weeks after randomisation
- Number of treatment emergent infusion site reactions during 16 weeks after randomisation
- Number of treatment emergent hypoglycaemic episodes classified both according to the American Diabetes Association definition and Novo Nordisk definition during 16 weeks after randomisation:
 - Overall
 - Daytime and nocturnal hypoglycaemic episodes (00:01-05:59 inclusive)
 - Hypoglycaemic episodes from start of meal until 1, 2, 4 hours and from 2 hours (exclusive) to 4 hours (inclusive) after start of meal
- Number of unexplained episodes of hyperglycaemia (confirmed by SMPG) during 16 weeks after randomisation
- Change from baseline 16 weeks after randomisation in clinical evaluations:
 - Physical examination
 - Electrocardiogram (ECG)
 - Vital signs (blood pressure, pulse)
 - Fundus photography/fundoscopy
- Change from baseline 16 weeks after randomisation in central laboratory assessments:
 - Haematology (haemoglobin, haematocrit, erythrocytes, thrombocytes, and leucocytes)
 - Biochemistry (total protein, creatinine, alanine aminotransferase (ALT), aspartate aminotransferase (AST), alkaline phosphatase (AP), sodium, potassium, albumin, and total bilirubin)
 - Urinalysis (for blood, protein, and ketones)
- Change from baseline 16 weeks after randomisation in body weight and body mass index (BMI)
- Number of change-of-infusion-sets per week during 16 weeks after randomisation
- Number of Subjects with at least one non-routine change-of-infusion-sets categorised by reasons for change-of-infusion-sets during 16 weeks after randomisation

5 Trial design

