8.3.2.3 Change of infusion set and reservoir

Infusion sets (Medtronic Quick-Set[®], Medtronic Mio[®], Medtronic Silhouette[®] or Medtronic SureT[®] (Easy-set®)) and reservoirs (1.8/3.0 mL) will be provided by Novo Nordisk. Infusion sets and reservoirs will be dispensed at site visits indicated in the flowchart in section 2. The type of infusion set and size of reservoir should be recorded in the eCRF at each dispensing visit.

The Subjects should be instructed to routinely change infusion set in intervals not exceeding 3 days (2 days for SureT[®] (Easy-set[®])). Infusion set and reservoir should be changed at the same time. The trial products should preferably be administered in the abdominal wall. The Investigator should ensure that the Subject is instructed in the following:

Protocol
Trial ID: NN1218-3854

CONFIDENTIAL

Date: 04 February 2016 | Novo Nordisk
Version: 4.0

• The infusion region chosen should remain unchanged throughout the trial

- The infusion site should be rotated within the same region
- The infusion set should preferably be inserted in the same way

The Subject should change infusion set and reservoir at the site under supervision by the Investigator at randomisation (Visit 6) and at end of treatment (Visit 22) due to the change from pre-trial insulin to trial product. The Investigator should evaluate the skin for any local skin irritation or skin infection at every visit at the clinic. Any abnormal clinically significant findings should be recorded as an infusion site reaction, as detailed in section 8.3.3.3.

The Subject should be instructed to record all infusion set change in their diary. Investigator should ensure that instructions for change are being followed by reviewing the CareLink Report. The review must be documented by signing the CareLink Report. Infusion set changes can be considered as a 'routine change' or 'non-routine change'.

Routine change

A routine change of the infusion set and reservoir is defined as a regular change performed in no more than 3-days intervals (2 days for SureT®(Easy-set®)). Infusion set change at site in the morning the day before randomisation (Visit 6) and end of treatment (Visit 22) are considered a routine change. All infusion set changes due to Subject's decision and not due to any problem with the pump, the infusion set or glucose values (e.g. inconvenient location of infusion set) must be considered a routine change.

Non-routine change

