A non-routine change is defined as any change of infusion set and reservoir not fulfilling the criteria for a routine change.

Protocol		Date:	04 February 2016	Novo Nordisk
Trial ID: NN1218-3854	CONFIDENTIAL	Version:	4.0	
TITEN T TITLE 1 1 1 1 1 0 0 1 0 0	CONFIDENTIAL	C	Tr: 1	

UTN: U1111-1118-2480 CONFIDENTIAL Status: Final Page: 56 of 149

Infusion sets and reservoirs must be replaced if any change in the insulin solution or occlusion is perceived by the Subject, e.g. because of a pump alarm indicating an occlusion or other observations pointing towards obstruction of the insulin flow. For every perceived occlusion the Subject must:

• Check the perceived occlusion with an air shot of at least 10 units of insulin performed using the pump's manual bolus option

Collection of infusion set change information

All infusion set changes from Visit 2 to Visit 22 will be collected in the Subjects' diary. For all infusion set and reservoir changes the Subject must record the following in the diary:

- The date and time of change
- Was the infusion set and reservoir change considered a routine change (Yes/No)?

In case the above question is answered "Yes" and the infusion set is changed prior to the 3 days (2 days for SureT[®](Easy-set[®]), the Subject should confirm that the change was not due to any of the reasons listed below.

In case the above question is answered "No" the Subject must choose one main reason from the below ("a" to "f") and record the following in the diary.

Was the change due to any of the following:

- a) A perceived occlusion by the Subject
 - Was an air shot performed? (Yes/No)
 - Was there any insulin flow when an air-shot was performed (Yes/No)?
 - Did a 'No delivery' alarm sound (Yes/No)?
 - Was there a visible plug obstructing the flow (Yes/No)?
- b) Changes in the **insulin solution in the infusion set or reservoir** (e.g. any visual change in colour or presence of particles)?
- c) Any problems related to the **infusion set** (e.g. leakages, dislodging of infusion set, large air bubbles etc.)?
- d) Any **infusion site reactions** (The Subject should be instructed to contact the site in case of any infusion site reactions; please see section 8.3.3.3)
- e) Any technical issues with the pump (Yes/No)
 - Did an alarm sound (Yes/No)?
 - If "Yes", specify the alarm

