1.1 Trial information

This is a double-blind, randomised, multicentre, multinational, active controlled, treat-to-target, parallel group trial with a 4-week run-in and a 16-week treatment period comparing the effect and safety of continuous subcutaneous insulin infusion (CSII) of fast-acting insulin aspart versus NovoRapid® in adult subjects with type 1 diabetes mellitus (T1DM). Subjects entering the trial will stay on their own insulin pump.

The total duration of the trial is approximately 26 weeks split into the following periods (see [Figure 1-1](#)):

- ≤ 2-week for screening period
- A 4-week run-in period primarily for reinforcement of subject training in trial procedures, diabetes education and collecting baseline assessments
- A 16-week double-blinded treatment period
- A 7-day and 30-day follow-up period

Note: Prior to randomisation and after end of treatment subjects are on marketed product.

Baseline is defined as randomisation.

Figure 1-1 Trial design

Up to 50% of the eligible subjects will be allowed to wear their own real-time continuous glucose monitoring (CGM) device during the entire course of the trial. The remaining enrolled Subjects will not be allowed to wear a CGM device except for three pre-specified periods. During these periods a

blinded CGM device will be handed out to all subjects by the Investigator, including subjects wearing their own CGM. Randomisation is stratified according to the use of own real-time CGM.

The primary objective is to confirm the effect of continuous subcutaneous insulin infusion (CSII) treatment with fast-acting insulin aspart in terms of glycaemic control by comparing it to CSII treatment with NovoRapid[®], in adults with Type 1 Diabetes Mellitus (T1DM), using a non-inferiority approach.

The secondary objectives are to confirm superiority of CSII treatment with fast-acting insulin aspart compared to CSII treatment with NovoRapid[®] in adults with T1DM, in terms of:

- Postprandial glucose regulation (meal test)
- Overall glycaemic control (HbA_{1c})
- Postprandial glucose excursions (1,5-anhydroglucitol)
- Time spent in low interstitial glucose (CGM)

To compare the effect and safety of CSII treatment with fast-acting insulin aspart vs. CSII treatment with NovoRapid[®] in adults with T1DM.

For further details see the trial protocol.

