Data on-treatment emergent hypoglycaemic episodes are presented in terms of the number of Subjects with at least one event (N), the percentage of Subjects with at least one event (%), the number of events (E) and the event rate per 100 years of exposure (R). Separate summaries are made by severity considering all episodes, nocturnal and daytime episodes using Novo Nordisk and ADA classified episodes. All episodes will also be summarised by category, including summaries in relation to time since start of meal, as occurring within the following time intervals:

- During first 1, 2 and 4 hours after the start of the meal
- Between 1 (exclusive) to 2 hours (inclusive) after start of meal
- Between 2 (exclusive) to 3 hours (inclusive) after start of meal
- Between 3 (exclusive) to 4 hours (inclusive) after start of meal
- Between 2 (exclusive) to 4 hours (inclusive) after start of meal

Non-treatment emergent hypoglycaemic episodes will be listed.

The number of treatment emergent severe or BG confirmed hypoglycaemic episodes (all, daytime, nocturnal, 1 hour, 2 hour, 4 hour, 1 (exclusive) to 2 hours (inclusive), 2 (exclusive) to 3 hours (inclusive), 3 (exclusive) to 4 hours (inclusive), and 2 (exclusive) to 4 hours (inclusive) after start of the meal) will be analysed based on the FAS using a negative binomial regression model with a log-link function and the logarithm of the time period in which a hypoglycaemic episode is considered

treatment emergent as offset. The model will include treatment, strata (two levels based on use of own CGM or not), previous insulin use (three levels: NovoRapid[®], Apidra[®], Humalog[®]), and region as factors. To the extent where data allow, separate analyses will be performed for all severe episodes.

Number of unexplained episodes of hyperglycaemia (confirmed by SMPG)

The number of unexplained episodes of hyperglycaemia will be summarised in a frequency table. Unexplained hyperglycaemia is defined as a confirmed PG value ≥ 16.7 mmol/L (300 mg/dL) and is unexplained (i.e. no apparent medical, dietary, insulin dosage or pump failure reason). The percentage of Subjects with unexplained hyperglycaemia will be presented.

Unexplained hyperglycaemic episodes will be defined as treatment emergent if the onset of the episode occurs on or after the first day of IMP administration after randomisation and no later than one day after the last day on IMP.

Physical examination

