For each Subject this is calculated as the total number of infusion sets used divided by the actual duration of the randomised treatment period in days, multiplied by seven. It will be summarised for each treatment using descriptive statistics.

Number of Subjects with at least one non-routine change categorised by reasons for change

The percentage of Subjects with at least one non-routine change will be presented, categorised by reasons for change, in a frequency table by treatment.

3 Changes to the statistical analyses planned in the protocol

General considerations

It has been clarified how data collected at visit 22A and 22B are handled.

Statistical analysis

It has been clarified that type 1 error will only be controlled for the primary estimand.

In the sensitivity analysis 2) for change from baseline in HbA_{1c} it has been clarified that baseline HbA_{1c} is still included in the analysis as a covariate.

In the statistical analysis in the protocol it is not clear if missing values or values for subjects discontinuing treatment/withdraw from trial should be imputed. Some of the following changes have been implemented to account for this issue.

In the sensitivity analysis for change from baseline in HbA_{1c} it has been changed from subjects withdrawing from trial to subjects with an imputed value at week 16 to be aligned with the primary analysis.

In the statistical sensitivity analysis 3b) for change from baseline in HbA_{1c} copy reference has been changed to conditional imputation, and for 3c) jump to reference has been changed to unconditional imputation to clarified the method used.

It has been clarified that the statistical analysis 4) will be repeated as for the confirmatory secondary endpoints.

For change from baseline in 1-hour PPG increment (meal test) it has been clarified how the endpoint is derived, which is aligned with the other endpoints derived from the meal test. To align with the primary analysis it has been changed so values at week 16 are imputed for subjects with missing values instead of imputing values for subjects withdrawn from trial, and the imputations are based on subjects in the NovoRapid[®] arm with non-missing values instead of completers in the NovoRapid[®] arm.

For the statistical analysis of change from baseline of time spent in low IG (≤ 3.9 mmol/L) it has been clarified that the corresponding baseline value will be included as covariate.

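### Non-routine infusion-set changes are summarised only as the percentage of subjects with at least one, so repeat events in the same subject are not shown

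*SAP*

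**What the plan says.** Protocol 4.2.3.5 names the endpoint as "Number of Subjects with at least one non-routine change-of-infusion-sets categorised by reasons for change-of-infusion-sets during 16 weeks after randomisation". SAP 2.4.2.2 analyses it in exactly that form: "The percentage of Subjects with at least one non-routine change will be presented, categorised by reasons for change, in a frequency table by treatment". No number of events, rate or model is planned for it.

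The data are richer than the summary. Protocol 8.3.2.3 states that "All infusion set changes from Visit 2 to Visit 22 will be collected" in the diary, each with date, time and whether it was routine. For a change that was not routine, the subject gives one main reason from six, (a) to (f): perceived occlusion, a change in the insulin solution, a problem with the set, a site reaction, a technical pump issue, or persistent high glucose. The category is defined by exclusion: "A non-routine change is defined as any change of infusion set and reservoir not fulfilling the criteria" for a routine one.

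The other infusion-set endpoint in SAP 2.4.2.2 is sets per week: all sets used over the time on randomised treatment, scaled to seven days.

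Two other recurrent safety outcomes in the same section get more. For hypoglycaemia the SAP gives, besides the number and percentage of subjects, "the number of events (E) and the event rate per 100 years of exposure (R)", and a negative binomial model for severe or BG confirmed episodes. Treatment-emergent adverse events also get event numbers and rates.

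**The concern.** Set changes recur often. The routine instruction is "The Subjects should be instructed to routinely change infusion set in intervals not exceeding 3 days" (2 days for Sure-T), and the trial has "A 16-week double-blinded treatment period". Each subject therefore has several dozen occasions on which a change may be non-routine. A yes/no per subject discards everything after the first event in a category, so two arms can have similar percentages while one has many more events among the affected subjects.

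This matters because the trial belongs to a programme seeking a pump indication (Protocol 3.2). Protocol 12.7.2 asks the data monitoring committee to look at possible set occlusions. Protocol 18.2 names technical pump problems as a potential route to hyperglycaemia and ketoacidosis. How often sets fail or appear blocked, by arm, is a natural question for the trial report, and the planned table does not answer it.

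**Working it through.** **The plan's own figures.** The documents give no number or rate for non-routine changes, so there is no figure on this endpoint to reproduce. The one planning quantity used below is 225 per arm (SAP 2.1). It checks out: a two-sample t-test with difference 0.9, SD 3.4 and two-sided 5% gives 80.0% power, as stated.

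**Occasions per subject.** 16 weeks = 112 days. At 3-day intervals there are at least 112/3 = 37.3 changes; for Sure-T at 2 days, at least 112/2 = 56.

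**Repeat events, at any rate.** Suppose 30% of each arm are affected, with 1.5 events per affected subject in one arm and 4 in the other (illustrative). The planned table shows 30% vs 30%. The rates are 0.30 × 1.5 = 0.45 and 0.30 × 4 = 1.20 per subject, a ratio of 2.7.

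**Loss of sensitivity to a rate difference.** Assume negative binomial counts with mean μ per subject and dispersion k (variance μ + kμ²), and a true rate ratio of 1.5.

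- P(at least one) = 1 − (1 + kμ)^(−1/k)
- Rate comparison: SE(log RR) = √[(1/μ₀ + 1/μ₁ + 2k)/225], power = Φ(log 1.5/SE − 1.96)
- Yes/no comparison: SE = √[(p₀(1−p₀) + p₁(1−p₁))/225], power = Φ((p₁−p₀)/SE − 1.96)

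Worked case, μ₀ = 5% × 37.3 = 1.87 and k = 1, so μ₁ = 2.805:

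- Percentages: 1 − 1/2.87 = 65.2% and 1 − 1/3.805 = 73.7%. SE = 0.0432, (0.737 − 0.652)/0.0432 = 1.98, power 51%.
- Rate: SE = √[(0.535 + 0.357 + 2)/225] = 0.1134, 0.4055/0.1134 = 3.58, power 95%.

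| Assumed events per subject, k = 1 | Subjects with ≥1 | Yes/no power | Rate power |
|---|---|---|---|
| 0.2 | 16.7% vs 23.1% | 40% | 47% |
| 0.75 (2% of 37.3 changes) | 42.9% vs 52.9% | 58% | 84% |
| 1.87 (5% of 37.3 changes) | 65.2% vs 73.7% | 51% | 95% |

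With k = 2 at 1.87 events, the powers are 33% and 79%. The rate has the higher power in every case tried, but the gap is small when events are rare (27% vs 29% at 0.1 events, k = 1).

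**Does sets per week recover the signal?** If a share q of changes is non-routine and these fall evenly within the 3-day interval, the mean interval is 3 − 1.5q days. Sets per week are then 7/(3 − 1.5q). Doubling q from 5% to 10% moves this from 7/2.925 = 2.39 to 7/2.85 = 2.46, a rise of 2.6%. A doubling of non-routine changes would barely show.

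**The case against.** A reader might infer that, over some 37 changes, the percentage must approach 100% in both arms and so make a real increase look like near-equality. The documents do not support that. They give no non-routine rate, and the ceiling matters only if the rate is high. With homogeneous subjects and 37 changes, a doubling shrinks below 5 percentage points only from about 7.7% of changes; at 1% vs 2% of changes it shows as 31% vs 53%. Variation between subjects keeps the percentage lower still. At a mean of 1.87 and k = 1, a doubling appears as 65% vs 79%, which a yes/no comparison would detect with about 91% power. The table is also split by reason, and each of the six categories lies further from the ceiling than the total. Protocol 3.1.2 reports no microscopically confirmed occlusions in a 6-week pump trial. Perceived occlusion is a broader category, but that result offers no support for frequent events.

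Nor is this an error or inconsistency: the SAP matches the endpoint as the protocol names it. There is no planned test, so the power figures do not describe a decision in the plan. Related safety information comes by other routes: site reactions are recorded as adverse events and so receive event rates, unexplained hyperglycaemic episodes are counted, and the data monitoring committee reviews possible occlusions.

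All of this stands, and it limits the size of the point. It does not remove it. None of these routes reports how many perceived occlusions, set problems or insulin-solution changes led to a set change in each arm.

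**Conclusion.** The point holds as a gap in a descriptive safety summary. The planned table shows how many subjects had a non-routine change but not how many changes there were, although the data to show both are collected. The loss of repeat events is certain; it follows from the definition of the summary. The loss of sensitivity to a rate difference is conditional: modest if a category averages about 0.2 events per subject, substantial from about 0.75 upwards. That grading rests on assumed means, dispersion 1 to 2, a rate ratio of 1.5 and nearly complete 16-week exposure. No confirmatory conclusion depends on this endpoint. The change is still worth making because the question is central to pump use and the cost is small.

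**What to change.** In SAP 2.4.2.2, keep the percentage table and add, for on-treatment non-routine changes, the number of events (E) and the rate per exposure time (R), overall and for each reason (a) to (f). Use the N, %, E, R layout already specified for hypoglycaemia. Count events and exposure over the same period, so that changes recorded during run-in, or in the diary after trial product has been stopped, do not enter.

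Where data allow, add a supportive negative binomial rate ratio with 95% CI for all non-routine changes and for perceived occlusion. Use the factors of the hypoglycaemia model (treatment, own-CGM stratum, previous insulin, region) and log on-treatment time as offset. Label it as descriptive.

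Cost: one extra table and reuse of a model already specified, with no new data collection. The downside is a further estimate outside the type I error control, which the label should make clear.
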